# 4.0 Objectives

Objectives specific to the current study are to:

- 1. Determine accuracy (sensitivity and specificity) of automated sickling test to detect HbS, compared to gold standard HPLC, and to conventional solubility test
- Determine whether SCD, SCT and healthy individuals can be classified using the automated sickling test that leverages machine learning on images of blood films under hypoxia
- Validate accuracy (>95% sensitivity and specificity) of lateral-flow assays (HemoTypeSC and Sickle SCAN) to detect SCD/SCT, and of Gazelle variant test to detect SCD, SCT, and β-thalassemia; and determine if low-cost techniques can potentially replace HPLC/electrophoresis tests in rural and remote settings

Long-term objectives of the overall project are to:

- 1. Implement trained machine learning algorithm to classify SCD, SCT and healthy individuals during screening tests in Nepal
- 2. Implement relevant low-cost point-of-care techniques in rural and remote communities of Nepal using insights and conclusions from current study

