# Evaluation of low-cost techniques for detecting sickle cell disease and $\beta$ -thalassemia in Nepal

# 1.0 Background

## 1.1 Sickle cell disease

Sickle cell disease (SCD) is a collection of inherited blood disorders, and is a multisystem disorder affecting nearly every organ in the body [1]. The disease primarily causes erythrocytes or red blood cells (RBCs) to be distorted and rigid due to polymerization (e.g. during deoxygenation), often changing them to crescent or sickle shaped cells [2]. Other cascading effects include hemolytic anemia, blockage of microvasculature (capillaries and small blood vessels), episodes of acute illness (such as vaso-occlusive pain crisis or sickle cell crisis), and progressive organ damage [3], [4]. The chances of survival and quality of life drastically increase with early diagnosis, newborn screening, penicillin prophylaxis, pneumococcal immunization, blood transfusion, hydroxyurea treatment, hematopoietic stem-cell transplantation, and education about disease severity and complications [1], [4].

SCD is one of the most common monogenic diseases worldwide and results from mutations in the  $\beta$ -globin gene [1], [3]. The most common and severe form of SCD is sickle cell anemia (SCA), caused by the inheritance of  $\beta^S$  alleles or the variant HbS (hemoglobin S or sickle hemoglobin) genes from both parents – resulting in the homozygous form HbSS, instead of the normal homozygous form HbAA. Another form of SCA is HbS/ $\beta^0$  thalassemia, caused by the inheritance of a  $\beta^0$  thalassemia mutation from one parent and an HbS gene from another, resulting in no normal HbA and a majority of HbS. The heterozygous form HbAS, known as sickle cell trait (SCT), affects millions of people worldwide and is usually not associated with hematological abnormalities [2]. On the other hand, compound heterozygous conditions are associated with mild to severe clinical courses and are also categorized as SCD. Some compound heterozygous conditions include HbS with hemoglobin C or HbC (HbSC), HbS with  $\beta$ -thalassemia (HbS/ $\beta^0$ -thalassemia or HbS/ $\beta^+$ -thalassemia), and HbS with other  $\beta$  globin variants (e.g. HbSD and HbSOArab) [1], [3], [4].

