# 5.0 Endpoints/Outcomes

The study has non-clinical endpoints (endpoints not relating to how a person feels, functions or survives, but which are objective indicators of biological processes) [44], with minimal intrinsic value to the participants of the current study, since most of the participants in the study will already know the diagnosis of SCD or SCT. However, the non-clinical endpoints are strongly associated with a meaningful clinical outcome of determining optimal screening alternatives for rural and remote communities.

**Primary endpoint/outcome**: Characterization of accuracy (sensitivity and specificity) of low-cost techniques, such as automated sickling test (standard sickling test enhanced using low-cost microscopy and machine learning), solubility test, HemoTypeSC, Sickle SCAN, and Gazelle Hb Variant test, for detecting sickle cell disease, sickle cell trait, and β-thalassemia, based on comparison with the gold standard test (HPLC).

**Secondary endpoint/outcome**: Training and testing of machine learning algorithm using deidentified images collected of blood films during sickling test. Assessment of whether a microscopy / machine learning based classification approach is suitable for deployment in rural areas in Nepal.

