## 6.3 Statistical Analysis Plan

Considering HPLC as the reference test, the sensitivity, specificity, positive predictive value (PPV) and negative predictive value (NPV) of the index tests or low-cost techniques (automated

sickling test, HbS solubility test, HemoTypeSC, Sickle SCAN, and Gazelle Hb variant test) will be evaluated.

For each case, the following definitions apply:

- True positive (TP): indicates a positive result for both the index test and the reference test
- True negative (TN): indicates a negative result for both the index test and the reference test
- False positive (FP): indicates a positive result for the index test, but a negative result for the reference test
- False negative (FN): indicates a negative result for the index test, but a positive result for the reference test

The following metrics will be calculated using the total number of TP, TN, FP, and FN:

Sensitivity = 
$$\frac{TP}{TP + FN} \times 100\%$$
  
Specificity =  $\frac{TN}{FP + TN} \times 100\%$   
 $PPV = \frac{TP}{TP + FP} \times 100\%$   
 $NPV = \frac{TN}{TN + FN} \times 100\%$ 

The metrics (sensitivity, specificity, PPV, and NPV) for the index tests will be calculated for the following two categories:

- 1. **Detection analysis by hemoglobin variant** (HbA, HbS, HbC, β-thalassemia): Heterozygous or homozygous forms containing a particular hemoglobin variant in both the index test and the reference test are true positive results for that variant. Test results lacking a particular hemoglobin variant in both index and reference tests, irrespective of other variants present, are true negative results for that variant. The following hemoglobin variants will be analyzed for the index tests.
  - HbS Solubility: HbA, HbS
  - Automated sickling: HbA, HbS
  - HemoTypeSC: HbA, HbS, HbC
  - Sickle SCAN: HbA. HbS. HbC
  - Gazelle Hb Variant: HbA, HbS, HbC, β-thalassemia
- 2. **Detection analysis by phenotype**: In this analysis, the metrics for homozygous and heterozygous states will be calculated differently. The following phenotypes will be analyzed for the index tests.
  - Automated sickling: HbAA, HbAS, HbSS, Overall
  - HemoTypeSC: HbAA, HbAS, HbSS, (HbAC, HbSC, HbCC), Overall
  - Sickle SCAN: HbAA, HbAS, HbSS, (HbAC, HbSC, HbCC), Overall
  - Gazelle Hb Variant: HbAA, HbAS, HbSS, HbS/β-thalassemia, HbA/β-thalassemia, Hbβ/β-thalassemia, (HbAC, HbSC, HbCC), Overall

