  - HbS Solubility: Not applicable, since solubility test can only identify the hemoglobin variant but not the homozygosity or heterozygosity

Any data that is excluded from the analysis, due to indeterminate results, missing data, withdrawal of consent, or any other reason, will be reported.

A total of around 120 participants – around 20 individuals with SCD (HbSS), 20 individuals with SCT (HbAS), 20 individuals with sickle cell /  $\beta$ -thalassemia compound heterozygous form (HbS/ $\beta$ -thalassemia), 20 individuals with  $\beta$ -thalassemia (Hb $\beta$ / $\beta$ -thalassemia), 20 individuals with  $\beta$ -thalassemia trait or carrier form (HbA/ $\beta$ -thalassemia), and 20 healthy individual participants (HbAA) – will be recruited for the study.

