### 7.2 Inclusion and Exclusion Criteria

#### 7.2.1 Inclusion Criteria

Since the techniques evaluated in the study aims at detecting sickle cell disease (SCD), sickle cell trait (SCT), and  $\beta$ -thalassemia, the following number of participants will be included in the study:

- 20 individuals with SCD (HbSS)
- 20 individuals with SCT (HbAS)
- 20 individuals with sickle cell/β-thalassemia compound heterozygous form (HbS/β-thalassemia)
- 20 individuals with β-thalassemia (Hbβ/β-thalassemia)
- 20 individuals with β-thalassemia trait or carrier form (HbA/β-thalassemia)
- 20 healthy individual participants or normal participants (HbAA, participants without any known hemoglobin disorders, such as SCD, SCT or β-thalassemia)

Participants older than 1 year of age at the time of drawing blood will be eligible. Signed and dated consent or assent forms will be required by the participants or their parents/guardians.

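### Objective 3 sets a >95% validation bar, but the analysis plan gives only point estimates, with no confidence interval and no rule for when the bar is met

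*Combined protocol and SAP*

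**What the plan says.** Section 4.0, third objective: "Validate accuracy (>95% sensitivity and specificity) of lateral-flow assays (HemoTypeSC and Sickle SCAN) to detect SCD/SCT, and of Gazelle variant test". The same bullet continues with the aim to "determine if low-cost techniques can potentially replace HPLC/electrophoresis tests in rural and remote settings".

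Section 5.0 words the primary endpoint more modestly, as "Characterization of accuracy (sensitivity and specificity) of low-cost techniques", and sets no threshold.

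Section 6.3 defines true and false positives and negatives against HPLC and then states: "The following metrics will be calculated using the total number of TP, TN, FP, and FN". Four formulas follow. There is no confidence interval, hypothesis test or success criterion. Metrics are planned by hemoglobin variant and by phenotype. For the lateral-flow assays the phenotype list is, for example, "HemoTypeSC: HbAA, HbAS, HbSS, (HbAC, HbSC, HbCC), Overall".

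On exclusions, Section 6.3 says: "Any data that is excluded from the analysis, due to indeterminate results, missing data, withdrawal of consent, or any other reason, will be reported".

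Recruitment is about 120 participants, in six groups of 20: HbSS, HbAS, HbS/β-thalassemia, Hbβ/β-thalassemia, HbA/β-thalassemia and HbAA. Section 12 supports the group size on feasibility alone. Section 6.1 adopts the STARD 2015 checklist to improve the reporting of findings.

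**The concern.** A numerical bar needs a rule that says when it has been cleared. Without one, the investigators could choose after seeing the data between a bare estimate, a one-sided limit and a two-sided limit. Those choices give different answers at these group sizes.

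The consequence is practical. The same bullet ties the result to replacing HPLC, and the long-term objectives in Section 4.0 look to field implementation based on this study's conclusions. Under the plan as written, 20 correct out of 20 could be reported as validated above 95% although the data are compatible with a sensitivity in the mid-80s.

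Two lesser choices can also move a result across 95%: how unreadable index-test results enter the calculation, and how the β-thalassemia groups count for assays that do not detect β-thalassemia.

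**Working it through.** **Inputs from the documents.** Six groups of 20 give 6 × 20 = 120, which reproduces the stated total. No alpha, power, expected accuracy or interval width is given, so 20 per group cannot be derived further. Denominators:
- One phenotype: 20 positives, and 100 negatives if every other group counts.
- SCD read to include HbS/β-thalassemia: 20 + 20 = 40 positives and 80 negatives.
- HbS at variant level: HbSS + HbAS + HbS/β-thalassemia = 60 positives and 60 negatives.
- β-thalassemia at variant level: HbS/β + Hbβ/β + HbA/β = 60 positives and 60 negatives.

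**Assumptions of this check.** A 95% confidence level, one- or two-sided, and the true accuracies named below.

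**Reading 1: the point estimate decides.**
- n = 20: 19/20 is exactly 95.0% and does not exceed 95%, so only 20/20 passes. The pass probability is p^20: 0.95^20 = 0.358 and 0.90^20 = 0.122.
- n = 60: 57/60 is exactly 95.0%, so 58/60 is needed. P(X ≥ 58) is 0.417 at a true 95% and 0.053 at a true 90%.

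**Reading 2: an exact (Clopper-Pearson) lower limit must exceed 95%.** With no errors the limit is α^(1/n), where α is 0.025 (two-sided) or 0.05 (one-sided). For 20/20, 0.025^(1/20) = 0.832 and 0.05^(1/20) = 0.861.

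| Result | Two-sided | One-sided |
|---|---|---|
| 20/20 | 83.2% | 86.1% |
| 40/40 | 91.2% | 92.8% |
| 59/60 | 91.1% | 92.3% |
| 60/60 | 94.0% | 95.1% |
| 99/100 | 94.6% | 95.3% |
| 100/100 | 96.4% | 97.1% |

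The smallest error-free denominator that excludes 95% solves 0.95^n ≤ α: n = 59 one-sided (0.95^59 = 0.0485) and n = 72 two-sided (0.95^72 = 0.0249).

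**Unreadable results.** Take 20 positives, one unreadable and the rest correct. Excluding it gives 19/19 = 100%; counting it as not correct gives 19/20 = 95.0%, which misses the bar on the point estimate. On the interval reading both fail at this size (19/19 has a two-sided limit of 82.4%). At variant level with a one-sided limit the answer flips: 59/59 gives 95.05% and 59/60 gives 92.3%. The documents give no unreadable rate.

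**β-thalassemia groups, lateral-flow phenotype metrics.** Section 1.6 says these assays detect HbA, HbS and HbC; Section 13 says they do not detect β-thalassemia. Suppose there are no other errors, and b of the 20 HbS/β-thalassemia participants read as HbSS and 20 − b as HbAS.
- All other groups as negatives: HbSS specificity is (100 − b)/100 and HbAS specificity is (80 + b)/100. The lower of the two is at most 90% (at b = 10), and 80% at b = 0 or 20.
- β-thalassemia groups left out: both are 40/40.
- SCD including HbS/β-thalassemia: an HbSS reading is then a true positive for SCD, and SCD specificity has 80 negatives.
- HbAA specificity moves likewise: 40/40 with these groups left out, or 80/100 if the 20 HbA/β-thalassemia participants read as HbAA.
- Overall runs from 60/60 (β-thalassemia groups left out) to 60/120 (all counted as discordant).

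**The case against.** The strongest defence is that the primary endpoint is characterization, that STARD 2015 will be followed, and that this is an estimation study whose size was set by feasibility. Some of that stands: nothing here shows the data to be unusable or calls for more participants. But the endpoint wording does not cancel the stronger objective, and the documents adopt STARD for reporting without stating an interval or criterion.

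Three stronger readings are tempting, and the documents do not support them.

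- A reader might infer that the plan ignores unreadable results. It does not: Section 6.3 names indeterminate results as a reason for exclusion and promises to report exclusions, so exclude-and-report is the natural reading. What remains is that accuracy is then conditional on a readable result, and no second analysis shows the effect.
- A reader might infer that phenotype negatives are undefined. The general definitions in Section 6.3 allow a one-versus-rest reading, since an HPLC result of HbS/β-thalassemia is not HbSS. It is implicit, however, and Section 1.1 states that "compound heterozygous conditions are associated with mild to severe clinical courses and are also categorized as SCD", while Sections 6.3 and 7.2.1 label the SCD group as HbSS. Detection of SCD/SCT by the lateral-flow assays could also be read simply as HbS present, where the variant-level negatives are expressly defined.
- A reader might infer that a >95% claim is out of reach throughout. It is not: 100 negatives can support one for specificity, and 60/60 supports one on a one-sided limit.

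**Conclusion.** The concern holds for the missing interval and decision rule; the other two matters are clarifications. On the point estimate alone, a test truly at 95%, which does not exceed the bar, passes 36% of the time with 20 positives and 42% with 60; one truly at 90% passes 12% and 5%. On an exact 95% lower limit, phenotype sensitivity cannot meet the bar with 20 or 40 positives. Sixty positives meet it only at 60/60 and one-sided. With 100 negatives, 100/100 meets it on either limit and 99/100 one-sided only.

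The figures assume full recruitment, independent participants and a conventional 95% level; the documents fix none of the interval choices. The specificity shift for the lateral-flow assays further assumes that they otherwise read HbA and HbS without error. This should be changed before analysis. It affects what may be claimed rather than whether the data can be used.

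**What to change.** 1. **Section 4.0.** Reword Objective 3 to estimate sensitivity and specificity with exact 95% confidence intervals, in line with the primary endpoint in Section 5.0. Treat 95% as a reference value.
2. **Section 6.3.** Add exact intervals for every variant and phenotype metric. Do not report a test as validated >95% unless the lower limit exceeds 95%, and state in advance whether that limit is one- or two-sided. State that it cannot be reached for phenotype sensitivity with 20 per group.
3. **Unreadable results.** Beside the analysis that excludes them, report sensitivity and specificity with unreadable index results counted as not correct (false negative if HPLC-positive, false positive if HPLC-negative), and give their number by group.
4. **β-thalassemia groups.** State how the three groups count in the lateral-flow phenotype and Overall metrics. Keep this consistent with one definition of SCD (HbSS only, or including HbS/β-thalassemia), and report the HbS/β-thalassemia group on its own line.

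The cost is wording in two sections and no extra participants. The downside is that a >95% claim will be available less often. For example, 60/60 occurs with probability 0.99^60 = 0.547, about 55%, if true sensitivity is 99%, and 0.98^60 = 0.298, about 30%, if it is 98% (both assumed values).

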# 5.0 Endpoints/Outcomes

The study has non-clinical endpoints (endpoints not relating to how a person feels, functions or survives, but which are objective indicators of biological processes) [44], with minimal intrinsic value to the participants of the current study, since most of the participants in the study will already know the diagnosis of SCD or SCT. However, the non-clinical endpoints are strongly associated with a meaningful clinical outcome of determining optimal screening alternatives for rural and remote communities.

**Primary endpoint/outcome**: Characterization of accuracy (sensitivity and specificity) of low-cost techniques, such as automated sickling test (standard sickling test enhanced using low-cost microscopy and machine learning), solubility test, HemoTypeSC, Sickle SCAN, and Gazelle Hb Variant test, for detecting sickle cell disease, sickle cell trait, and β-thalassemia, based on comparison with the gold standard test (HPLC).

**Secondary endpoint/outcome**: Training and testing of machine learning algorithm using deidentified images collected of blood films during sickling test. Assessment of whether a microscopy / machine learning based classification approach is suitable for deployment in rural areas in Nepal.

# 6.0 Research Design

# 6.1 Research Plan and Design

The overall project has two phases:

- 1. Vancouver trials (September 2022 April 2023): With the help from hematologists and hematopathologists at BC Children's Hospital (BCCH) and St. Paul's Hospital (SPH), we plan to test the following screening techniques on patients with sickle cell disease (SCD) and sickle cell trait (SCT), and healthy participants:
  - a. Low-cost screening
    - i. Sickling test with low-cost automated microscope (such as Octopi microscope) and automated screening with machine learning
    - ii. HbS solubility test
    - iii. Commercial point-of-care assays (HemoTypeSC and Sickle SCAN)
    - iv. Gazelle Hb variant test
  - b. Gold standard test: HPLC, for determining the accuracies of low-cost screening techniques
- 2. **Nepal trials (October 2022 April 2023):** With help from [name], CP Nepal, UBC sickle cell team, and local lab technicians and health workers, we plan to screen the communities (e.g. in Nepalgunj) using the following:
  - a. Low-cost screening
    - i. Sickling test with low-cost automated microscope (such as Octopi microscope) and automated screening with machine learning
    - ii. Sickling test with traditional microscope (conventional manual screening used in Nepal)
    - iii. HbS solubility test
    - iv. Commercial point-of-care assays (HemoTypeSC and Sickle SCAN)
    - v. Gazelle Hb variant test
  - b. Gold standard test: HPLC, for determining the accuracies of low-cost screening techniques

This research protocol relates to the Nepal trials. There will be two ethics application submitted concurrently for the Nepal trials – one to the UBC Research Ethics Board and another to the Nepal Health Research Council.

To improve the transparency and completeness of reporting the findings (e.g. for publications resulting from this study), the checklist from the Standards for Reporting of Diagnostic Accuracy Studies or STARD 2015 will be followed [45]. The STARD 2015 guidelines was developed by experts to help reduce bias in diagnostic accuracy studies and to ensure that their reporting includes necessary information.

# 6.2 Duration of Study

The study is expected to commence in October/November of 2022 as soon as all regulatory requirements have been fulfilled including clinical Research Ethics Board approval. The recruitment, consent and sample analysis is expected to take 1-3 months from study commencement.

## 6.3 Statistical Analysis Plan

Considering HPLC as the reference test, the sensitivity, specificity, positive predictive value (PPV) and negative predictive value (NPV) of the index tests or low-cost techniques (automated

sickling test, HbS solubility test, HemoTypeSC, Sickle SCAN, and Gazelle Hb variant test) will be evaluated.

For each case, the following definitions apply:

- True positive (TP): indicates a positive result for both the index test and the reference test
- True negative (TN): indicates a negative result for both the index test and the reference test
- False positive (FP): indicates a positive result for the index test, but a negative result for the reference test
- False negative (FN): indicates a negative result for the index test, but a positive result for the reference test

The following metrics will be calculated using the total number of TP, TN, FP, and FN:

Sensitivity = 
$$\frac{TP}{TP + FN} \times 100\%$$
  
Specificity =  $\frac{TN}{FP + TN} \times 100\%$   
 $PPV = \frac{TP}{TP + FP} \times 100\%$   
 $NPV = \frac{TN}{TN + FN} \times 100\%$ 

The metrics (sensitivity, specificity, PPV, and NPV) for the index tests will be calculated for the following two categories:

- 1. **Detection analysis by hemoglobin variant** (HbA, HbS, HbC, β-thalassemia): Heterozygous or homozygous forms containing a particular hemoglobin variant in both the index test and the reference test are true positive results for that variant. Test results lacking a particular hemoglobin variant in both index and reference tests, irrespective of other variants present, are true negative results for that variant. The following hemoglobin variants will be analyzed for the index tests.
  - HbS Solubility: HbA, HbS
  - Automated sickling: HbA, HbS
  - HemoTypeSC: HbA, HbS, HbC
  - Sickle SCAN: HbA. HbS. HbC
  - Gazelle Hb Variant: HbA, HbS, HbC, β-thalassemia
- 2. **Detection analysis by phenotype**: In this analysis, the metrics for homozygous and heterozygous states will be calculated differently. The following phenotypes will be analyzed for the index tests.
  - Automated sickling: HbAA, HbAS, HbSS, Overall
  - HemoTypeSC: HbAA, HbAS, HbSS, (HbAC, HbSC, HbCC), Overall
  - Sickle SCAN: HbAA, HbAS, HbSS, (HbAC, HbSC, HbCC), Overall
  - Gazelle Hb Variant: HbAA, HbAS, HbSS, HbS/β-thalassemia, HbA/β-thalassemia, Hbβ/β-thalassemia, (HbAC, HbSC, HbCC), Overall
  - HbS Solubility: Not applicable, since solubility test can only identify the hemoglobin variant but not the homozygosity or heterozygosity

Any data that is excluded from the analysis, due to indeterminate results, missing data, withdrawal of consent, or any other reason, will be reported.

A total of around 120 participants – around 20 individuals with SCD (HbSS), 20 individuals with SCT (HbAS), 20 individuals with sickle cell /  $\beta$ -thalassemia compound heterozygous form (HbS/ $\beta$ -thalassemia), 20 individuals with  $\beta$ -thalassemia (Hb $\beta$ / $\beta$ -thalassemia), 20 individuals with  $\beta$ -thalassemia trait or carrier form (HbA/ $\beta$ -thalassemia), and 20 healthy individual participants (HbAA) – will be recruited for the study.

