# 1.7 Current initiatives in Nepal

The University of British Columbia (UBC) Sickle Cell Project, a part of the UBC Global Health Initiative, aims to spread awareness of sickle cell disease and to help with screening patients in rural communities of Nepal, while collaborating with local non-profit organizations such as Creating Possibilities (CP) Nepal. CP Nepal has operated since 2006, with an overarching goal of protecting and advocating for the rights of marginalized women and children in Nepal. Since 2015, the UBC Sickle Cell Project have collaborated with CP Nepal, and sent teams of 6-12 medical students annually to conduct screening, diagnosis and education of SCD in the district of Dang, Nepal. So far, four sustainable health posts have been set up in rural parts of Western Nepal to screen for SCT and SCD.

In 2015/2016, a study conducted by the UBC Sickle Cell team and CP Nepal found the prevalence of SCD and SCT to be around 10% within the Tharu community in Dang, Nepal, based on screening approximately 3000 individuals aged 6 months to 40 years [43]. In some parts of Western Nepal, such as Nepalgunj, the prevalence was found to be as high as around 25% [11]. Since many of the studies in Nepal do not include newborn screening, the prevalence of the disease could be higher in rural communities of Nepal, and extensive screening and diagnosis programs are required to accurately identify and treat affected patients. The current study to evaluate performance of low-cost detection techniques is inspired by efforts of teams such as UBC Sickle Cell team and CP Nepal. The UBC Sickle Cell team and CP Nepal plan to help and support the Nepal study.

When the UBC Sickle Cell team conducted their initial study in 2015/2016, they focused on the sickling test for screening and had to send blood samples from some of the patients to India for confirmatory electrophoresis tests, since the gold standard HPLC tests were not available anywhere in Nepal. Over the last few years, some hospitals and clinics across Nepal have

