#### 7.1.1 Participants with HbS and/or β-thalassemia

All the participants with HbS and/or  $\beta$ -thalassemia (all participants excluding healthy volunteers) will be identified using the records of Bheri Hospital or Mount Sagarmatha Polyclinic in Nepalgunj. Records for the last 2-3 years will be accessed. Patients (and if applicable, their guardians) will be informed about the research trial and if willing to participate, informed consent will be obtained. The initial contact by delegate will happen either during in-person clinic visits or through telephone. Upon consent/assent, blood samples (3-4 mL) will be drawn for the research study (in addition to the routine bloodwork, if applicable).

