# 7.8 Neural Network Training and Testing

Data manipulation and analysis will be done through Python. All software to be utilized is opensource and does not have commercial implications. In order to optimize the screening algorithm, multiple neural network configurations will be tested and compared. All the models tested for classification will use existing pre-trained models that have applications in image classification. In each case, the acquired images will be split into three groups, consisting of training data (around 80%), validation data, (around 10%) and testing data (around 10%). The data will be used to train the neural network using a pre-trained supervised machine learning model, whereby the images are input and the parameters of the network are optimized to classify images by hemoglobin phenotype. The test data will test the performance of the trained network on images that have not been used for training. We will use the neural networks most commonly used for medical image classification, such as EfficientNet, ResNeXt, ResNet-50, DenseNet, and Xception. When possible, training will occur locally on the laboratory computer at UBC. For networks that require additional computing power, UBC ARC Sockeye or Compute Canada will be used.

All the machine learning algorithms will only include de-identified data, such as images of blood films and hemoglobin phenotype (such as sickle cell trait or HbAS). Personal identifying information, such as participant names, will not be associated with any of the data used for analysis or stored online.

Cloud computing facilities, such as those from Compute Canada, will be utilized to train and test machine learning algorithms on the final dataset of images. Compute Canada is a cloud computing service provided by Digital Research Alliance of Canada (the Alliance) to Canadian research institutions. The servers and clusters (e.g. Cedar cluster located in BC) will be accessed using Secure Shell Protocol (SSH). For the analysis (before sharing the data publicly), de-identified images may be stored securely in UBC servers or in servers for Compute Canada.

The de-identified data (such as images of blood films and associated de-identified data like hemoglobin phenotype) will be deposited in an online public repository, such as Federated Research Data Repository.

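### Section 6.3 takes HbS PPV and NPV from quota-fixed counts (about 50% HbS by design), so they are not predictive values at the roughly 10% to 25% prevalence that the protocol cites

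*Combined protocol and SAP*

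**What the plan says.** Section 6.3 plans "the sensitivity, specificity, positive predictive value (PPV) and negative predictive value (NPV) of the index tests or low-cost techniques", with HPLC as the reference. On the source of the numbers it says: "The following metrics will be calculated using the total number of TP, TN, FP, and FN". PPV is TP/(TP+FP) and NPV is TN/(TN+FN).

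The same section fixes the case mix. Its quotas begin with "around 20 individuals with SCD (HbSS), 20 individuals with SCT (HbAS), 20 individuals with sickle cell" and β-thalassemia combined, and continue with 20 for β-thalassemia, 20 for β-thalassemia trait and 20 healthy people, about 120 in all. Section 7.2.1 repeats the six groups, ending with "20 healthy individual participants or normal participants". Under section 7.1.1, everyone except the healthy volunteers "will be identified using the records of Bheri Hospital or Mount Sagarmatha Polyclinic in Nepalgunj"; the volunteers respond to posters (section 7.1.2).

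On prevalence, section 1.7 says that a 2015/2016 study "found the prevalence of SCD and SCT to be around 10% within the Tharu community in Dang, Nepal", and that in parts of Western Nepal, "such as Nepalgunj, the prevalence was found to be as high as around 25" percent.

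Neither section 6.3 nor the limitations in section 13 adjusts PPV or NPV for prevalence, or says that they depend on the quotas.

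**The concern.** PPV and NPV depend on how common the condition is among those tested. Here that share is a recruitment decision: investigators who chose other quotas would obtain other predictive values from the same tests. Section 2.0 says that the results should inform test choice in rural, remote and low-resource settings, and section 6.1 describes the Nepal phase as community screening. A health worker who reads a PPV from this study will take it as the chance that a positive result is real. At the prevalences the protocol cites, that chance could be well below the reported figure.

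**Working it through.** **Inputs.** Quotas of about 20 in each of six phenotypes (6.3, 7.2.1). Prevalence p of about 10% and up to about 25% (1.7; the 25% is read from context as HbS prevalence). Illustrative sensitivity (Se) and specificity (Sp): 95/95, the floor of the target above 95% for the lateral-flow and Gazelle tests (4.0); 99/99, an assumption; and the lower and upper solubility-test figures, 45/90 and 99/99.9 (1.5).

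**The plan's own figure.** 6 × 20 = 120, as stated. HbS is present in HbSS, HbAS and HbS/β-thalassemia: (20 + 20 + 20)/120 = 50%.

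**Formulas.**

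PPV = Se·p / [Se·p + (1 − Sp)(1 − p)]

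NPV = Sp(1 − p) / [Sp(1 − p) + (1 − Se)p]

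At 95/95 and p = 0.10, PPV = 0.095/(0.095 + 0.045) = 67.9% and NPV = 0.855/(0.855 + 0.005) = 99.4%. At p = 0.25, PPV = 0.2375/(0.2375 + 0.0375) = 86.4% and NPV = 0.7125/(0.7125 + 0.0125) = 98.3%.

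| Se/Sp (%) | PPV at 50 / 25 / 10% | NPV at 50 / 25 / 10% |
|---|---|---|
| 95/95 | 95.0 / 86.4 / 67.9 | 95.0 / 98.3 / 99.4 |
| 99/99 | 99.0 / 97.1 / 91.7 | 99.0 / 99.7 / 99.9 |
| 99/99.9 | 99.9 / 99.7 / 99.1 | 99.0 / 99.7 / 99.9 |
| 45/90 | 81.8 / 60.0 / 33.3 | 62.1 / 83.1 / 93.6 |

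With no observed false positives, the PPV point estimate is 100% at every prevalence. With no false negatives, the same is true of NPV.

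**Uncertainty.** Jeffreys 95% intervals for PPV, drawing Se and Sp from Beta(x + 0.5, 60 − x + 0.5):

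- 57/60 on both: 45% to 88% at p = 0.10; 71% to 96% at p = 0.25.
- 60/60 on both: 73% to 100% and 89% to 100%.

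**Does the direction hold if the case mix differs?** Of the 60 HbS-negative participants, 40 have β-thalassemia or its trait. Take Se = 95% and Sp = 57/60.

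- For community PPV to equal the raw 95%, the false-positive rate must be 0.05p/(1 − p): 0.00556 at p = 0.10 and 0.01667 at p = 0.25.
- If all three false positives fall among the 40, their rate is 3/40 = 0.075. The raw value is then not overstated if those forms make up at most 0.00556/0.075 = 7.4% of community HbS-negatives at p = 0.10, or 0.01667/0.075 = 22% at p = 0.25.
- If all three fall in HbAA (Sp = 17/20 = 85%) and all community HbS-negatives are HbAA, PPV is 0.095/(0.095 + 0.135) = 41.3% at p = 0.10 and 0.2375/(0.2375 + 0.1125) = 67.9% at p = 0.25.
- For NPV, take Sp = 95% and Se = 57/60. If all three false negatives are HbAS (Se = 17/20 = 85%) and all community HbS is HbAS, NPV at p = 0.25 is 0.7125/(0.7125 + 0.0375) = 95.0%, the same as the raw value.

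**The case against.** The strongest reply is that nothing turns on these values. The primary outcome is sensitivity and specificity (5.0), and PPV and NPV appear in no hypothesis, objective or endpoint. The formulas are correct, the plan never calls the results community values, and the quotas are printed in the same section, so a reader could convert them. Community implementation is listed as a long-term objective, apart from those of this study (4.0). All of this stands and lowers the importance. It does not remove the problem: 6.3 commits to PPV and NPV for every index test, and following it as written yields numbers set by recruitment.

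The cited prevalences are also soft. The 10% comes from work that relied mainly on the sickling test, with only some samples sent for confirmation, and section 1.7 says the true figure could be higher. It does not say what kind of sample lies behind the 25%. That argues for showing results at more than one stated value.

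Three stronger readings are tempting, and the documents do not support them:

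- *Raw values hide differences between tests.* This is true of PPV only: 99/99 and 95/95 differ by 4.0 points at 50% and 23.8 at 10%. For NPV it reverses, from 4.0 points to 0.5. At a common prevalence the order of tests does not change.
- *The comparison of automated sickling with the solubility test is undermined.* Objective 1 compares sensitivity and specificity, which this point does not touch.
- *The automated sickling test has a known further distortion.* Section 7.8 splits acquired images, with about 10% for testing. Raw values depend on that set's make-up, but how images are grouped by participant is not stated, so no size follows. With similar image numbers per participant, a split by image would stay near 50%.

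**Conclusion.** The point holds as a missing adjustment and label, of minor to moderate importance. For tests run on all participants, raw HbS PPV and NPV describe a sample that is about half HbS by design. That share is approximate, since quotas are around 20 and study HPLC or exclusions may shift it.

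If sensitivity and specificity carry over and are below 100%, raw PPV is too high and raw NPV too low. At 95/95 the PPV gap is 8.6 points at 25% prevalence and 27.1 at 10%; the NPV gap is 3.3 and 4.4 points the other way. At 99/99.9 the PPV gap is under one point.

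A reader might infer that the published PPV is bound to be inflated. The documents do not establish that, because the study mix of HbS-negatives and HbS-positives need not resemble a community's. For β-thalassemia, section 1.4 gives only a share of hemoglobinopathies, so neither size nor direction can be worked out.

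**What to change.** Amend section 6.3 as follows:

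1. Report HbS PPV and NPV by Bayes' formula from the estimated sensitivity and specificity at 10% and 25% prevalence, both described as approximate. Give 95% intervals that carry the uncertainty in both; Jeffreys Beta draws are one option and still work at 60/60.
2. State the assumption that sensitivity and specificity carry over to the community.
3. Keep the 2×2 counts. Label any raw PPV and NPV as set by the study quotas, including those for β-thalassemia and single phenotypes, for which the documents give no population prevalence.
4. Use the same stated prevalences for the automated sickling test, and note that its raw values also depend on the make-up of its image test set.

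The cost is some SAP wording and a few lines of code, with no new participants or data. The downside is a less favourable PPV unless specificity is near 100%, with wide intervals (about 45% to 88% at 10% prevalence with 57/60 on both), resting on approximate prevalences and an untested carry-over assumption.
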